2.0 Objectives*

Aim 1. *Examine the feasibility of recruitment (e.g., how many OAs need to be screened to recruit the sample?), especially during the COVID-19 pandemic, and*

acceptability of technologies and procedures for use among OAs in low-income settings.

Aim 2. *Examine the associations among fall risk appraisal, body composition, and physical activity.*

H2.1: Rational FRA is associated with higher levels of PA and skeletal muscle mass, and lower levels of percent of body fat and BMI.

H2.2: Incongruent FRA is associated with higher levels of PA and skeletal muscle mass, and lower levels of percent of body fat and BMI.

H2.3: Irrational and congruent FRAs are associated with lower levels of PA and skeletal muscle mass, and higher levels of percent of body fat and BMI.

Aim 3. Determine the dynamic relationships between fall risk appraisal, body composition, physical activity and behavioral changes related to fear of falling.

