(FRA), a condition in which there is a discrepancy between perceived fall risk (levels of FOF) and physiological fall risk (balance performance).^{17, 18} Measuring FRA in OAs can be challenging due to self-report bias and cognitive deficit.^{19, 20} Using both subjective and objective measures provides better fall risk assessment among OAs.^{20, 21} Thus, we developed a *fall risk appraisal matrix*, a graphical grid categorizing levels of FOF and balance performance into four quadrants (Fig 1): **1) rational FRA** (low FOF and normal balance), **2) incongruent FRA** (low FOF despite poor balance), **3) irrational FRA** (high FOF despite normal balance), and **4) congruent FRA** (high FOF and poor balance).¹⁷ In our pilot study (N=102), we measured FOF by a questionnaire and balance performance using a portable and novel force balance plate (BTrackS Balance System; **BBS**). We found that 40% of OAs had maladaptive FRA. Of this group, 19% with incongruent FRA and 30% with irrational FRA reported falling in the past year.¹⁷ OAs with congruent FRA were 3.29 times more likely to fall than those with rational FRA.²² However; our sample included only 11% of low-income OAs.

3.3

Maladaptive FRA may impede low-income OAs participation in PA and can result in social isolation.^{20, 23} Irrational FRA serves as a barrier, creating an irrational fear that inhibits OAs from staying active. Conversely, incongruent FRA can act as an impediment to OAs' safety by fabricating a sense of wellbeing when more caution is warranted. Rational FRA is a crucial component of regular engagement in PA.²⁴ However, research has not examined the association between FRA and PA among low-income OAs. We will examine the association between FRA and PA among low-income OAs.

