If he/she indicates that she/he is ready and wants to participate in this research study, she/he will be asked to complete the questionnaires such as socio-demographics and fear of falling.

Procedure for contacting participants for timepoint 2:

Experimental procedures for both groups

We will assess the static balance performance using the BBS. Participants will take off their shoes and stand as still as possible on the balance plate with hands on their hips and eyes closed for 2-3 minutes. Participants will then complete the

dynamic balance performance test using the sit to stand by full standing up from a chair as many as possible within 30 seconds.

Participants will be stratified by the FRA matrix.¹⁷ We will continually evaluate across four groups (rational/ incongruent/ irrational/ congruent) to maintain equal cell distribution (30 OAs/group)*.

- 1) rational FRA: low FOF [Short Fall Efficacy Scale International (short FES-I) score ≤ 10] and aligned with normal balance (BBS score = 0-30).
- 2) incongruent FRA: low FOF (short FES-1 score ≤ 10) despite poor balance (BBS score= 31-100).
- 3) irrational FRA: high FOF (short FES-I score > 10) whereas normal balance (BBS score= 0-30).
- 4) congruent FRA: high FOF(short FES-I score > 10) and poor balance (BBS score= 31-100).¹⁷

**Please note: This is not an intervention study and subjects will not be assigned to the study group.*

They will perform the hand-grip strength and sit to stand tests. Hand-grip strength will be measured in kilograms (kg) as maximal isometric force achieved on a hand-grip dynamometer. This test will be administered with participants sitting in a chair with feet flat on the floor and the elbow bent at 90°. The dynamometer will be placed in the hand and adjusted so the palm side of the grip will be at the palm, and the front end will be lined up between the joints of the medial and distal phalanges. The grip size will be adjusted so that the second metacarpals were flat with a 90° bend at the knuckles. Participants will be asked to squeeze the strength gauge as hard as possible for 3–5 seconds. Three trials on each hand will be performed with 30-s of rest given between trials. Participants will complete the sit to stand by full standing up from a chair as many as possible within 30 seconds.⁷⁸

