Aim 2 hypotheses are: **1)** Rational FRA is associated with higher levels of PA and skeletal muscle mass, and lower levels of percent of body fat and BMI, **2)** Incongruent FRA is associated with higher levels of PA and skeletal muscle mass, and lower levels of percent of body fat and BMI, **3)** Irrational and congruent FRAs are associated with lower levels of PA and skeletal muscle mass, and higher levels of percent of body fat and BMI. General summary statistics will be presented for continuous data, and percentages will be presented for categorical data. Participant demographic data will be summarized. Analyses will be performed without adjusting for any covariates, followed by the analyses adjusted for age, comorbidities, depressive symptoms, and fall history. Age, the number of comorbidities and the number of falls in the past year will be selected as covariates in the selected model because of their association with FRA, body composition, and PA. Data from InBody770 (e.g., BMI) and ActiGraph (e.g., steps/day) could be modeled as continuous.

Regression models or one-way ANOVA will be used to examine differences in continuous variables (e.g., BMI, steps/day) across the four groups (rational, incongruent, irrational, and congruent FRAs), and categorical variables (e.g., comorbidities) will be tested using Chi-Squared tests. Rational FRA group will set as a base group, and the other three groups (incongruent, irrational, and congruent FRAs) will be compared with this base group. Whenever feasible, models will be adjusted for age, sex, day order, wear time (minutes/day), and the number of fall history. These following variables will add one by one to evaluate the role of each: mobility problems (Y/N), depression (score or category), fall risk (high/low), perceived general health (score of category), medication use (Y/N), and comorbidities (Y/N). A final model will include all significant potential variables to evaluate whether associations between FRA, body composition and PA, whenever feasible.

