Specific Aim 2 Sample Size and Power Analysis. There is no historical precedent and limited information to inform the sample size for this study; therefore, the sample size estimate was based on the variable of the BBS score in our pilot study. The standard deviations of the mean BBS scores in our pilot study were 7.91 in the high PA group and 7.78 in the low PA group (PA by self-report), assuming a two-tail alpha 0.05 and a power 0.8, the estimated total sample size N=120 would allow to sufficiently detect a mean difference about 5 between the two groups. Furthermore, to be able to compare the effect sizes of the different body composition and PA measures, we will perform post-hoc analyses to compare the mean values between the two groups of PA, adjusted for the age group.

Aim 3. Determine the dynamic relationships between fall risk appraisal, body composition, physical activity and behavioral changes related to fear of falling

We hypothesize that higher percentage body fat, and lower frequency and duration of physical activity are associated with fall risk appraisal and the associations vary between four groups. We will collect data at the 2nd timepoint and then a dynamic prediction model will be used to investigate their temporal, dynamic associations.

17.2

We will maintain a master list that will contain identifiable data and links the subject ID codes with the participant's information. The electronic version of this master list will be encrypted, password protected, and stored on a computer and is located in a restricted access room at the College of Nursing. The master list is the only document with identifiable data.

All research data, including identifiers and linking sheets, will be retained for at least 5 years after the study closure.

The de-identified data (such as balance performance test data will be password protected, encrypted, and stored on computers and external hard drives in the restricted access laboratory). The de-identified data will be kept indefinitely. The reason for keeping the de-identified data indefinitely is for scientific reproducibility and transparency.

17.3 NA

17.4

Efforts will be made to limit the use and disclosure of participants' personal information, including research study to people who have a need to review this information. We cannot promise complete secrecy.

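### The listed group comparisons set incongruent FRA only against rational FRA, so H2.2 has no pre-specified contrast with the groups predicted to be low

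*Combined protocol and SAP*

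**What the plan says.** Section 2.0 states three hypotheses under Aim 2, which the Study Summary makes the primary objective. H2.1 predicts higher physical activity (PA) and muscle mass, and lower body fat and BMI, for rational FRA. The next one uses the same terms: "H2.2: Incongruent FRA is associated with higher levels of PA and skeletal muscle mass, and lower levels of percent of body fat and BMI". The third reverses them: "H2.3: Irrational and congruent FRAs are associated with lower levels of PA and skeletal muscle mass", with higher body fat and BMI. None of the three names a reference group.

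Section 17.1 (Aim 2) gives the analysis: "Regression models or one-way ANOVA will be used to examine differences in continuous variables (e.g., BMI, steps/day) across the four groups". Rational FRA is the base, and "the other three groups (incongruent, irrational, and congruent FRAs) will be compared with this base group". No other FRA comparison is listed. The only post-hoc analyses are in the sample size paragraph and concern a different grouping: "we will perform post-hoc analyses to compare the mean values between the two groups of PA". Section 6.4 says enrolment will be watched "to maintain equal cell distribution (30 OAs/group").

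**The concern.** Four groups give six pairs. The plan lists three, all against rational. Rational vs irrational and rational vs congruent separate a group predicted high from a group predicted low, so they serve H2.1 and H2.3. The third, incongruent vs rational, sets two groups predicted high against each other. The two pairs that would show whether incongruent FRA stands above the groups predicted low are not listed.

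If the plan is followed as written, one of the three hypotheses on the primary objective has no directional test. Its expected result is a null difference from rational. A null difference at 30 per group is also common when incongruent FRA is not high. The contrast that matters could be taken from the fitted model later, but the choice of comparator would then be made after the data are seen.

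**Working it through.** **1. Match hypotheses to listed comparisons (PA and muscle mass; reverse for body fat and BMI).**

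| Pair | Predicted | Listed? |
|---|---|---|
| Rational vs irrational | high vs low | yes |
| Rational vs congruent | high vs low | yes |
| Rational vs incongruent | high vs high | yes |
| Incongruent vs irrational | high vs low | no |
| Incongruent vs congruent | high vs low | no |
| Irrational vs congruent | low vs low | no |

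The gap is in the text and depends on no effect size. The rest shows its size.

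**2. The plan's own figure.** The plan says that "the estimated total sample size N=120 would allow to sufficiently detect a mean difference about 5 between the two groups", for the BBS score in high and low PA groups, with SDs 7.91 and 7.78, two-sided alpha 0.05 and power 0.8. Pooled SD = sqrt((7.91² + 7.78²)/2) = 7.845. The normal formula gives n = 2 × (1.960 + 0.842)² × 7.845² / 5² = 38.7, so 39 per group and 78 in total. The 120 is not reproduced but more than covers that goal. It does not bear on this point, because it concerns neither FRA groups nor an H2.2 outcome.

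**3. Inputs for the FRA comparisons.** 30 per group (Section 6.4), no covariates, residual df = 120 − 4 = 116, two-sided 0.05, critical t = 1.981. The documents give no SD for PA or body composition by FRA group. The high-low gap d is therefore assumed: 0.5 SD, and 5/7.845 = 0.637 SD, the latter borrowed only as a scale. Means are in the order rational, incongruent, irrational, congruent. H2.2 true is (d, d, 0, 0). H2.2 false, with incongruent as low as the high-fear groups, is (d, 0, 0, 0).

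**4. Incongruent vs rational alone.** SE = sqrt(2/30) = 0.258 SD, so the noncentrality is 0.5/0.258 = 1.94 or 0.637/0.258 = 2.47, and power is 0.484 or 0.687. A non-significant result occurs 95% of the time if H2.2 is true. If H2.2 is false it occurs 1 − 0.484 = 52% or 1 − 0.687 = 31% of the time.

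**5. All three listed comparisons together.** The predicted pattern is irrational and congruent both significantly below rational, and incongruent not significantly different from it. Over 1,000,000 simulated trials:

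| Gap | H2.2 true | H2.2 false |
|---|---|---|
| 0.5 SD | 30% | 8% |
| 0.637 SD | 52% | 9% |

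**6. Overall F(3, 116).** Noncentrality = 30 × sum of squared deviations of the four means: 30d² if H2.2 is true (7.5 or 12.2), and 22.5d² if false (5.6 or 9.1). It rejects 61% or 83% of the time if true, and 48% or 70% if false. It is non-directional and does not isolate H2.2.

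**7. The unlisted contrasts.** Incongruent vs irrational and incongruent vs congruent have the SE of step 4, so each has 48% or 69% power. Both are significant in 32% or 54% of simulated trials. Incongruent vs the average of the two has SE = sqrt(1/30 + 1/60) = 0.224 SD and power 60% or 81%. If only one of the two groups is low, the averaged difference is d/2, and it is still significant 20% or 29% of the time.

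**The case against.** The strongest reply has four parts.

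- **The comparator is implied, and H2.2 is not alone in omitting it.** This stands. H2.1 and H2.3 name none either, and the three together point to high vs low. A reader might infer that H2.2 is singularly ill-formed. The documents do not support that: the wording is common to all three, and what is specific to H2.2 is the missing contrast.
- **The planned set already says something about H2.2.** This also stands. Step 5 shows the predicted pattern to be several times more frequent when H2.2 is true. But it rests on one non-significant result, with no equivalence margin, and never estimates incongruent against a low group.
- **The four-group regression yields the contrast.** It does, as a difference of two coefficients. The plan does not say that this will be done.
- **The background does not single out the high-fear groups.** Section 3.3 says "Irrational FRA serves as a barrier, creating an irrational fear that inhibits OAs from staying active", and a reader might take this as naming the comparator. But the same section says that maladaptive FRA, which by Section 3.2 includes incongruent FRA, may impede PA, and it makes no separate statement on PA in congruent FRA. The comparator follows from H2.3, not from the background.

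A reader might also infer that the investigators mean to count a null incongruent-vs-rational difference as support. No section says so.

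**Conclusion.** The point holds as a gap between hypothesis and analysis. The listed comparisons serve H2.1 and H2.3. They give H2.2 only a comparison whose expected value is about zero if H2.1 and H2.2 both hold, and neither that comparison nor the overall F test is a test of H2.2. It would go too far to say that the plan is silent on H2.2 or cannot address it: the planned set is partly informative (30-52% vs 8-9%), and the planned model contains what is needed.

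The percentages rest on 30 completers per group, equal variances, no covariate adjustment, no multiplicity adjustment and an assumed gap of 0.5 to 0.64 SD; they indicate scale only. Because the study is cross-sectional and the remedy is wording plus contrast statements, this is a cheap improvement and not a design fault.

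**What to change.** In Section 17.1, Aim 2:

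- State H2.2's comparator. H2.3 implies the high-fear groups, irrational and congruent. If the investigators mean another, they should name it and list the matching contrast.
- From the same four-group regression, pre-specify incongruent vs irrational and incongruent vs congruent for each outcome, with confidence intervals. Say in advance whether support for H2.2 requires both.
- Incongruent vs the average of the two may be added as a summary. It should not carry H2.2 alone, because it can be significant when only one of the groups is low.
- Keep the rational-base comparisons.
- State that a non-significant incongruent-vs-rational difference will not be read as support for H2.2.

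The cost is two more contrasts per outcome: eight for PA, muscle mass, body fat and BMI if each is a single measure. No new data or participants are needed. Unadjusted power is about 48-69% per contrast at the assumed gap, so the intervals will often be wide. How to adjust for multiplicity is a separate decision.

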3.0 Background*

3.1

[figure not shown]
More than 15 million (30%) OAs in the US have incomes below the 200% of poverty line.^{1, 2} Poverty rate increases with age, and is higher among women, Blacks and Hispanics, and individuals with poor health.¹ OAs who live in low-income communities are less likely to engage in PA,³⁻⁵ defined as any bodily movement produced by skeletal muscle that results in energy expenditure.⁶ Lack of PA is related to chronic conditions and reduced quality of life among low-income OAs.^{7, 8} Limited data suggest that OAs who overestimate their fall risk and report fear of falling (**FOF**) are less likely to participate in PA, and the association between FOF and PA intensity differs by fear severity.⁹ Changes in body composition also have a significant impact on functional capacity and quality of life.¹⁰ However; these studies have not included OAs from low-income settings, who are more likely to report falls in the prior year.¹¹ Recent systematic reviews found that most studies have not used objective measures of fall risk and PA.^{5, 12} We will use objective measures of body composition, balance performance, and PA among OAs from low-income settings.

Additionally, up to 50% of OAs who have FOF limit their daily physical activity (**PA**) because of the fear.¹³ The COVID-19 pandemic is causing increased fear and related to perceived risks for loved ones and health anxiety.¹⁴ Physical distancing and fear of the virus have led to reductions in OAs' use of routine healthcare and performing daily PA.¹⁵ With the high levels fear; individuals may not think rationally when reacting to COVID-19 and taking care of themselves.¹⁶

3.2

One-third of OAs have maladaptive **fall risk appraisal**

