6.2 Provide a description of all research procedures

We will administer the study instruments which consist of objective and subjective measures (see Table 1) for total 120 participants. Participants will complete questionnaires about OA's characteristics, socio-demographic, medical history, cognition, depressive symptoms, anxiety,

and FOF. We will also assess static balance performance using the BTrackS Balance System^{43, 44}, assess dynamic balance using a sit to stand test, assess body composition using the Bioelectrical Impedance Analysis device⁴², and assess handgrip strength test using a hand-grip dynamometer (JAMAR 5030J1). They will wear an accelerometer-based physical activity device for 7 consecutive days.

Table 1. Description of study variables and instruments

Variable	Instrument	Description
OA's Characteristics - Socio-demographics and medical history -Cognition - Depressive symptoms -Anxiety and day-to-day experiences	Self-report questionnaire - Memory Impairment Screen (MIS) ⁵¹⁻⁵³ -Patient Health Questionnaire-9 (PHQ-9) ^{54, 55} -Geriatric Anxiety Inventory-Short form (GAI-SF). ⁵⁶⁻⁵⁸	e.g., age, gender, living status, education level, socioeconomic status, perceived general health, comorbidities, FOF, frailty, fall risk, and social network. - The Memory Impairment Screen (MIS) is a widely used test of cognitive function and screening Alzheimer's disease among OAs. It is a 4-minute, four-item delayed free and cued recall memory test with controlled learning and high discriminative validity. The maximum score for the MIS is 8 and if score 5-8=no cognitive impairment and score ≤ 4 =possible cognitive impairment. -10 items (e.g., feeling tired) on a 4-point scale; measures symptoms of depression within the prior 2 weeks; Total scores range 0-27, scores ≥ 10 moderate depression. ⁵⁴ Cronbach's alpha=0.89 among OAs. ^{54, 55} - The GAI-SF is an abbreviated version of GAI comprising only five of the original items. The GAI-SF has good internal consistency, convergent and divergent validity, and was highly

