6.4 Screening, consent, and experimental procedures

Screening, consent for participants in Kinneret Sr Apartments

Staff from this site will introduce the researchers to older adults in Kinneret Sr Apartments for performing recruitment. Our team will meet with participants at a meeting room in Kinneret Sr Apartments. We will screen participants by asking their age and language (English or Spanish). We will also ask if they have a medical condition precluding balance test and/or physical activity (e.g., shortness of breath, unable to stand on the balance plate) or currently receiving treatment from a rehabilitation facility or have a metal implant. Finally, we will assess their cognition using the Memory Impairment Screen (MIS) test. It will take about 3-5 mins (total) per person.

We will complete the informed consent in a private and quiet place in Kinneret Sr. apartments for participants who meet the inclusion criteria. If the participant needs time to discuss taking part in this research study with family members, friends, and other care providers, we will reschedule a visit for completing surveys and tests.

If he/she indicates that she/he is ready and wants to participate in this research study, she/he will be asked to complete the questionnaires such as socio-demographics and fear of falling.

Procedure for contacting participants for timepoint 2:

Screening, consent for the general population (outside Kinneret)

Our team will meet with each participant (by appointment) in a private and quiet place at the UCF College of Nursing. Participants will complete a simple COVID-19 self-checker questionnaire before coming to the UCF campus. We will screen participants by asking their age and language (English or Spanish). We will also ask if they have a medical condition precluding balance test and/or physical activity (e.g., shortness of breath, unable to stand on the balance plate) or currently receiving treatment from a rehabilitation facility, or having a metal implant. Finally, we will assess their cognition using the Memory Impairment Screen (MIS) test. It will take about 3-5 mins (total) per person.

We will complete the informed consent in the participants who meet the inclusion criteria. If the participant needs time to discuss taking part in this research study with family members, friends, and other care providers, we will reschedule a visit for completing surveys and tests.

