10.0 Inclusion and Exclusion Criteria*

10.1

We will screen individuals who will be eligible to participate based on the inclusion and exclusion criteria listed

10.2

Participants will be enrolled if they meet all of the following inclusion criteria: 1) ≥ 60 years of age; 2) no marked cognitive impairment [Memory Impairment Screen (MIS) score ≥5], 3) speak English or Spanish, and 4) live in Kinneret Sr. Apartments.

Exclusion criteria:1) a medical condition precluding balance test (e.g., unable to stand on the balance plate) and/or PA (e.g., shortness of breath; feeling pressure when performing PA); or 2) currently receiving treatment from a rehabilitation facility, or 3) have a metal implant.

10.3

We will exclude all the special populations:

- Adults unable to consent
- Individuals who are not yet adults (infants, children, teenagers)
- Pregnant women
- Prisoners

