13.0 Recruitment Methods

13.1 *Describe when, where, and how*

Approximately 150-200 older adults in Central Florida and Kinneret Sr Apartments will be screened to enroll 120 older adults in this study.

For the Kinneret Sr Apartments, staff from this site will introduce the researchers to older adults for performing recruitment. Our team will meet with participants in a common room or a meeting room in Kinneret Sr Apartments for screening participants.

In the general population, we will recruit them via social media, flyers, and word of mouth.

The research team will follow the UCF COVID-19 Human Subject Research Standard Safety Plan and maintain a log that tracks screening, eligibility, contact, and recruitment.

Approximately 60 adults of the 120 adults who participated at timepoint 1 will be contacted for enrollment for timepoint 2. We will contact participants who elected to be contacted for future studies in their original consent form.

13.2 *Source to subjects*

-Kinneret Sr Apartments, Orlando, FL (Please see Table in Section 24 for the source of subjects).

-General population who are living in Central Florida

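### Aim 2 pools two recruitment streams with no term for source, leaving the fall risk appraisal contrasts open to confounding of unknown size and direction

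*Combined protocol and SAP*

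**What the plan says.** Section 13.1 sets one enrolment target for two sources: "Approximately 150-200 older adults in Central Florida and Kinneret Sr Apartments will be screened to enroll 120 older adults in this study". Section 13.2 lists the building and, separately, "General population who are living in Central Florida".

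The streams differ in route and place. Kinneret residents are introduced to the team by building staff and seen in a room there. For the others, "In the general population, we will recruit them via social media, flyers, and word of mouth", and section 6.4 adds: "Our team will meet with each participant (by appointment) in a private and quiet place at the UCF College of Nursing".

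The Aim 2 text in section 17.1 compares the four FRA cells in one analysis, with the rational cell as reference. It contains four covariate lists:

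- age, comorbidities, depressive symptoms and fall history;
- age and the counts of comorbidities and of past-year falls;
- "Whenever feasible, models will be adjusted for age, sex, day order, wear time (minutes/day), and the number of fall history";
- variables tried one at a time (mobility, depression, fall risk, general health, medication, comorbidities), of which the significant ones go into the final model.

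Section 6.1 also says in general terms that participants' characteristics will be controlled for. It gives sex as the example and points to Fig. 2. Table 1 includes among those characteristics "socioeconomic status, perceived general health, comorbidities".

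Inclusion criterion 4 in section 10.2 reads "4) live in Kinneret Sr. Apartments".

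**The concern.** A confounder of the FRA contrasts has to be related both to FRA cell and to the outcome. Recruitment source could be both. One stream is residents of a single senior building. The other is volunteers who make contact themselves and attend an appointment on campus. Such groups may differ in activity, body composition, fear of falling and balance. The background section gives a partial reason to expect this: "OAs who live in low-income communities are less likely to engage in PA".

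The target of 30 participants per FRA cell gives no protection, because it balances the cell counts and not the mix of sources within each cell. If the mix differs, a contrast on steps per day or percent body fat contains part of the source difference, and a reader could not separate that part from an association with FRA.

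The general commitment in section 6.1 does not close the gap. It is not carried into section 17.1 by name for socioeconomic status, and recruitment source is not among the Table 1 variables at all.

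**Working it through.** The plan states no figure on this point: no expected split by source and no source effect. The check therefore has two parts, a reading of the covariate lists and an illustration with assumed inputs.

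**Covariate lists.** Source, site, income, education or socioeconomic status appears in 0 of the 4 lists in section 17.1. Fall history or fall count appears in 3 of the 4.

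**Inputs to the illustration.** Four cells of 30 (section 6.4); two-sided alpha 0.05 (section 17.1). Assumed: a difference in the Kinneret share between the rational and the compared cell of 20 points (for example 12 of 30 against 18 of 30) or 40 points (9 of 30 against 21 of 30), and a source effect D of 0.3, 0.5 or 0.8 within-source SD.

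**Formula.** With no true FRA association,

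spurious difference = (share in compared cell − share in rational cell) × D.

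Low end: 0.20 × 0.3 = 0.06 SD. High end: 0.40 × 0.8 = 0.32 SD.

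**Effect on the test.** A simulation with no FRA effect (4,000 runs per row) tested rational against congruent, with and without a binary source term:

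| Share difference | D (SD) | Spurious difference (SD) | False positives, no source term | With source term |
|---|---|---|---|---|
| 20 points | 0.3 | 0.06 | 6.0% | 5.8% |
| 20 points | 0.5 | 0.10 | 6.4% | 4.9% |
| 20 points | 0.8 | 0.16 | 9.3% | 5.1% |
| 40 points | 0.3 | 0.12 | 7.6% | 5.1% |
| 40 points | 0.5 | 0.20 | 10.4% | 4.3% |
| 40 points | 0.8 | 0.32 | 21.4% | 5.0% |

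With equal shares in all cells the rate without a source term was 4.4% to 5.4%, so there is no problem in that case. With the source term the average spurious difference was within 0.006 SD of zero in every scenario.

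**Hand check of one row** (40 points, D = 0.5). The outcome variance within a cell is 1 + 0.5² × 0.3 × 0.7 = 1.0525. The standard error is √(2 × 1.0525 / 30) = 0.265. The spurious difference is 0.20 / 0.265 = 0.75 standard errors, which gives a false-positive rate of about 11.7% by the normal approximation, close to the simulated 10.4%.

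**Scale.** Two cells of 30 have 80% power for a difference of about 0.74 SD. The range 0.06 to 0.32 SD is 8% to 43% of that.

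**Direction.** The incongruent cell is low fear with poor balance, and H2.2 expects higher activity and lower body fat there. If less active residents were over-represented in that cell, the distortion would run against H2.2. In the irrational and congruent cells the same over-representation would run with H2.3. No single direction covers all three contrasts.

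**The case against.** The other side has substance on several counts.

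- **Socioeconomic status is not ignored.** Section 6.1 commits to controlling for participants' characteristics, and Table 1 counts socioeconomic status among them. Fig. 2, cited there, is not in the text available to me and may name more. A reader might infer that the protocol overlooks socioeconomic status altogether; the documents do not support that. What stands is that section 17.1 does not name it.
- **The plan links income, not source, to activity.** The background sentence compares low-income communities with others, not Kinneret with the second stream. The title and Aim 1 concern low-income settings, and the amendment history describes the added recruits as low-income. The income gap may be small. However, section 10.2 has no income criterion, and differences in housing, route and site remain.
- **Existing covariates may absorb part of it.** Fall history, comorbidities, depression and perceived health are adjusted for or tested. The illustration gives no credit for these.
- **The routes may overlap.** Section 13.4 also puts flyers on boards in dining rooms, entrances and elevators.
- **There may be only one source.** Read literally, inclusion criterion 4 admits Kinneret residents only. It contradicts sections 6.4, 13 and 22.1, and the point depends on how that is resolved.
- **The inputs are assumed.** Section 13.2 refers to a table in section 24 for the source of subjects, which is not in the text available to me.

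These arguments limit how strongly the point can be put. None of them puts a source term into the model.

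**Conclusion.** The point holds as a gap in the prespecified models: two streams are pooled, and no Aim 2 covariate list names the source. It should be corrected, but it is a safeguard against possible confounding and not a demonstrated bias. It requires that both streams enrol, that their mix differs across FRA cells, and that source is related to activity or body composition after the planned adjustment. The range of 0.06 to 0.32 SD, with false-positive rates of about 6% to 21%, rests wholly on the assumed inputs and omits the planned covariates.

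A reader might infer that pooling favours the study's hypotheses. The documents do not support this: they give no source split by cell, and for the incongruent cell the distortion could oppose H2.2.

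**What to change.** In section 17.1:

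1. Enter recruitment source (Kinneret or general population) as a fixed covariate in every adjusted Aim 2 model, exempt from the rule that keeps only significant variables.
2. Tabulate FRA cell by source. If a cell comes almost entirely from one stream, say so, because adjustment then leans on the model.
3. Add the collected socioeconomic-status variable in a sensitivity model, which makes the commitment in section 6.1 explicit.

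Reconcile inclusion criterion 4 with sections 6.4, 13 and 22.1. If only Kinneret residents are enrolled, the source term is unnecessary.

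The cost is a few sentences and one degree of freedom in the main models. Stream is known at enrolment, so no new data are needed. In the simulation the standard error of the contrast with the source term was 0.26 to 0.27 SD at 20 to 40 points of imbalance, against 0.26 to 0.28 without it. At an extreme 60 points it rose to about 0.29, against 0.26 to 0.27.
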